## Methodology

At all sites, patient recruitment will occur through the following methods: identifying eligibility in medical records, in-house advertising, external community-based advertising, and use of the CHOIR database at Stanford University. Study coordinators will review the clinic schedule daily to identify eligible patients based on pain and opioid information available in the electronic medical record. Clinicians will discuss EMPOWER with patients and obtain permission from interested patients to be contacted by study staff. Study coordinators will then obtain informed consent and register participants in the CHOIR research learning health system database to initiate survey deployment. After completing the baseline survey, participants will be randomized to one of three intervention arms: (1) EMPOWER Taper Only (no behavioral treatment); (2) EMPOWER Taper + pain-CBT; or (3) EMPOWER Taper + CPSMP. Block randomization with variable block sizes, stratified by study site, will be utilized. The Executive Research Team, including the Principal Investigator and the data analytic team, will remain masked to intervention assignment throughout recruitment, enrollment, and data collection. Participants, EMPOWER clinicians, and study coordinators will be aware of intervention assignment. For the study flow diagram, see Figure 1.

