**Figure 1. Study Flow Diagram**

**Eligibility Criteria.** Inclusion criteria are: adults aged 18–85 years, diagnosed with chronic non-cancer pain (lasting at least six months), and actively taking prescription opioids (at least 10 MEDD) for at least three months at any of our seven study sites. Eligibility will not be restricted to specific pain conditions. Exclusion criteria include: clinician-determined moderate or severe opioid use disorder (OUD) as defined by a brief screening tool; inability to provide informed consent; inability to meaningfully participate in group interventions (e.g., due to cognitive impairment or lack of English fluency); or known disruptive behavior that could interfere with the group learning experience and treatment outcomes for the cohort. Patients with moderate to severe OUD will be referred for addictionology consult or triaged per local systems.

Patients with active substance use disorder (SUD) may enroll and local systems will refer them for SUD evaluation and treatment as clinically indicated. No special vulnerable populations will be recruited (e.g., children or patients pregnant at the time of enrollment). All research procedures will take place at the seven clinical sites, with data collection and some treatment elements occurring online.

**Consent Procedures.** Electronic consent will be administered through CHOIR^1 following completion of the screening visit. Participants will provide consent by entering their full name and date on the consent form webpage in CHOIR after reviewing the form with study staff. A copy of the consent form will be securely emailed to the participant. Two study sites (Phoenix Veterans Affairs Health Care System and Kaiser Permanente Oakland) will administer consent locally.

**Participant Compensation.** Participants will receive a \$25 Amazon gift card code for completing assessments at baseline, month 6, and month 12, and \$5 for completing weekly surveys from weeks 1–24 and monthly surveys from months 7–11 (29 total surveys). Total possible compensation for study participation is \$220. For participants who do not complete their 12-month survey and do not respond to any of the contact attempts made by the study team including the EMPOWER clinician we will offer an additional \$50 incentive for completing the last survey.

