***Monthly CHOIR surveys:*** Patients will be assessed monthly for satisfaction with the study, current opioid use, hospital or emergency medical visits, depressive symptoms, suicidality, and other factors that may indicate symptom worsening and require follow-up. Suicidality will trigger e-alerts to the prescribing clinician, site director, site coordinator, study manager, and the overall principal investigator. Site-specific messages will provide patients with instructions for non-emergency triage (e.g., calling the clinic for telephone or in-person follow-up) and emergency triage options in their community (e.g., calling 911), rapid contact with clinic staff, and crisis hotlines.

Weekly and monthly surveys will ensure careful monitoring of patients, triage of issues, and close connections with study staff and prescribing providers to enable rapid taper adjustments and address any additional needs. Study clinicians may securely access EMPOWER CHOIR via a web browser to review patient responses and coordinate participant activities. Comprehensive patient-reported survey batteries will be administered at baseline and at six and 12 months, including data on opioid use.

***Randomization.*** Each site will conduct a site-specific randomized controlled trial using a randomized design, allowing rapid accrual of patient cohorts (N=8–18 per cohort) assigned to the same intervention arm and timely delivery of behavioral interventions. Patients entering the study will be automatically assigned to the currently open intervention arm. The ordering of intervention arms will remain blinded to patients and clinicians, who cannot choose or direct group assignment. Study coordinators, while unblinded, will be trained to maintain clinician and patient blinding. After enrollment and baseline measures, group assignments will be revealed to participants. A statistician unaffiliated with patient care will create unique randomization schemes for each site, enabling prompt receipt of behavioral interventions for those assigned to such arms (ideally within two to ten weeks of taper initiation). Behavioral intervention timing will be recorded.

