#### **Sample Size Calculations and Study Power**

The power calculation is primarily based on the study aims for comparative effectiveness. The original power calculation was for  $N = 850$ , with  $N = 750$  patients completing the month-12 survey. The study sample size was later reduced to  $N = 489$  participants completing the month-12 survey ( $n = 163$  patients per intervention arm on average). As a result, the study's power is lower than initially planned but remains adequate for the objectives, summarized as follows:

*Hypothesis 1a.*  $N = 163$  Taper Only participants provide 80% power to confirm that the taper success rate is above 40% at a two-sided significance level of 0.05, when the true success rate is 51.5%.

*Hypothesis 1b.* Comparing the taper success rate between  $n = 140$  Taper Only participants with an initial dose  $< 200$  MEDD and  $n = 23$  Taper Only participants with an initial dose  $\geq 200$  MEDD, the expected 95% confidence interval (CI) for the difference in success rates is [-22%, 22%], assuming a true taper success rate of 50% independent of the initial dose. The width of the CI increases by only 24% due to the sample size reduction.

*Hypothesis 2a.*  $N = 163$  participants per intervention arm provide 80% power for detecting a taper success rate difference of 40% versus 53.5% at a two-sided significance level of 0.05.

*Hypothesis 2b.*  $N = 163$  participants per intervention arm yield an expected 95% CI of [-11%, 11%] for estimating the difference in taper success rates between the Taper + pain-CBT and Taper + CPSMP arms, assuming a taper success rate of 50% in both arms.

*Hypothesis 2c and 2d.*  $N = 163$  participants per intervention arm provide 80% power to detect a between-group difference of 0.311 standard deviation in the 12-month change of continuous outcomes using a two-sample t-test at a two-sided significance level of 0.05.

We also assume an annual drop off rate is less than 19% and we will include all drop outs in our ITT analyses. We will enroll a total of 594 patients to assure the minimum group size requirements for analysis of comparative effectiveness.

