#### **Statistical Analysis Plan**

*Aim 1:* Reduce or contain prescription opioid use while maintaining pain control.

*Hypothesis 1a:* We will estimate the proportion of patients achieving patient-centered opioid taper success and test whether this proportion exceeds 40% (treatment success estimate derived from Darnall et al.). We will estimate the binomial proportion of patients with opioid taper success and use the exact test to test whether the proportion is greater than 40%.

*Hypothesis 1b:* We will compare opioid tapering success rates among patients in different initial opioid dose categories: Low (10–49 MEDD), Moderate (50–89 MEDD), High (90–199 MEDD) and Super-High ( $\geq 200$  MEDD).

**Aim 2:** Examine the balance in key patient characteristics such as initial opioid dose, pain intensity, and functional measures separately for the three interventions arms. We will use Chi-square or Fisher's exact tests to compare success rates between opioid dose groups.

***Hypothesis 2a:*** We will compare the intervention success rate of 500 patients in behavioral intervention arms (pain-CBT and CPSMP) with 250 patients receiving patient-centered opioid tapering only (no behavioral intervention; Taper Only). We will use a Chi-square test to compare the success rate between groups. We will apply logistic regression to adjust for baseline covariates.

***Hypothesis 2b:*** We will estimate the difference in intervention success rates between pain-CBT and CPSMP arms using an intention-to-treat procedure and construct 95% CIs for the difference.

***Hypothesis 2c:*** We will compare changes in pain intensity, pain interference, and depression scores (baseline to 12 months) between the pain-CBT and Taper Only as well as between the pain-CBT and CPSMP arms using two-sample t-tests. We will apply an analysis of covariance based on multiple regression to adjust for baseline covariates.

***Hypothesis 2d.*** We will compare improvements in satisfaction with social roles and activities, and self-efficacy for Taper + CPSMP against Taper + pain-CBT and Taper Only.

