We will compare the intervention success rate between participants who received the behavioral interventions with participants who received Taper Only using Fisher's exact test. The difference in success rates between Taper + pain-CBT and Taper + CPSMP will be assessed with 95% confidence intervals (CI) to determine equivalence. Secondary outcomes—including pain intensity, pain interference, depression, self-efficacy, and satisfaction with roles and activities—will be compared between Taper + pain-CBT and Taper Only and between Taper + pain-CBT and Taper + CPSMP at months 6 and 12 using mixed effects model for repeated measurements regression. This analysis will incorporate baseline, month 6, and month 12 outcomes as dependent variables, with an unstructured variance-covariance matrix for within-subject correlations.

***Exploratory Hypothesis 2e:*** We will separately estimate the probability of opioid escalation by intervention arm (pain-CBT, CPSMP and Taper Only).

For exploratory hypotheses, the probabilities of opioid escalation by intervention group will be estimated and compared with Fisher's exact test. Post-hoc analyses will use logistic regression to examine associations between baseline characteristics and tapering success. There is no correction for multiple comparisons. Heterogeneity of treatment effects will be explored by splitting the population into training and validation sets of equal sizes. Logistic regression with lasso regularization will identify baseline features predicting tapering success in each intervention group. These models will be applied to testing sets to identify the subgroup with the highest predicted success under Taper + pain-CBT, and success rates will be compared across intervention arms within the subgroup. Intervention effects will be also estimated in predefined subgroups.

Heterogeneity of treatment effects will be explored for each intervention arm considering gender, age, race, initial opioid dose, baseline depression, and anxiety level.

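### Site is a randomization stratum, but the named taper-success test (H2a) and interval (H2b) do not use it: a minor improvement in SAP wording

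*Combined protocol and SAP*

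**What the plan says.** **Allocation.** The Methodology section states: "Block randomization with variable block sizes, stratified by study site, will be utilized". There are seven sites (Eligibility Criteria: "All research procedures will take place at the seven clinical sites"). The Randomization paragraph, later in the same section, adds a separate scheme for each site and describes cohorts of 8 to 18 placed in one arm: "Patients entering the study will be automatically assigned to the currently open intervention arm".

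**H2a analysis.** The Statistical Analysis Plan first names a Chi-square test: "We will use a Chi-square test to compare the success rate between groups". It then adds: "We will apply logistic regression to adjust for baseline covariates". The covariates are not listed. A later paragraph of the same section names a different test for the same contrast: "We will compare the intervention success rate between participants who received the behavioral interventions with participants who received Taper Only using Fisher's exact test".

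**H2b analysis.** The difference between pain-CBT and CPSMP is estimated "using an intention-to-treat procedure and construct 95% CIs for the difference", and the interval is later given the task of judging equivalence. No adjusted analysis is stated.

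Site does not appear in the analysis plan as a stratum, covariate or random effect. The power section works from 489 completers, on average 163 per arm, and does not mention site either.

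**The concern.** An analysis should normally follow the strata used in the randomization. The sites here include primary care, pain clinics, a VA system and closed payer systems, and tapering is individualized by local clinicians, so success rates may well differ between sites.

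If they do, the consequence depends on how patients are allocated:

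- **Arms balanced within site.** Between-site variation cancels out of the arm contrast, but the unstratified variance still counts it. The test is then conservative and the interval too wide.
- **Long same-arm cohorts.** The site mix can differ between arms by chance. Between-site variation then enters the contrast beyond what the unstratified variance allows, so the test may reject too often and the interval may be too narrow.

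The second case matters for H2b because its interval is meant to support an equivalence statement.

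**Working it through.** **Step 1. Reproduce the plan's figures.** Inputs from the power section: 163 completers per arm, 40% v 53.5%, two-sided 0.05. H2a pools the two behavioral arms, so the contrast is 163 v 326. (The H2a text still prints 250 and 500, which do not match the 489 completers now planned.)

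- Pooled rate = (163 × 0.40 + 326 × 0.535)/489 = 0.490.
- SE0 = √[0.490 × 0.510 × (1/163 + 1/326)] = 0.0480.
- SE1 = √[0.40 × 0.60/163 + 0.535 × 0.465/326] = 0.0473.
- Power = Φ[(0.135 − 1.96 × SE0)/SE1] = Φ(0.867) = 80.7%, against a stated 80%.
- H2b half-width = 1.96 × √(2 × 0.25/163) = 10.9 points, against a stated 11.

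Both figures reproduce without site.

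**Step 2. Arms balanced within site.** Let r be the within-site share of the outcome variance. Then:

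- actual alpha of the unstratified test = 2[1 − Φ(1.96/√r)];
- unstratified power = Φ[(0.135 − 1.96 × SE0)/(√r × SE1)];
- stratified power = Φ[(0.135 − 1.96 × √r × SE0)/(√r × SE1)].

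The between-site spread is an **assumption**: seven equal sites with site success rates spread on the logit scale. Example at logit SD 0.5, where r = 0.9446: alpha = 2[1 − Φ(2.017)] = 0.044; unstratified power = Φ(0.892) = 81.4%; stratified power = Φ(0.950) = 82.9%.

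| Logit SD | Taper Only site rates | H2a alpha, unstratified | H2a power, unstratified v stratified | H2b half-width, unstratified v stratified (points) | H2b coverage, unstratified |
|---|---|---|---|---|---|
| 0 | 40–40% | 0.050 | 80.7 v 80.7% | 10.9 v 10.9 | 95.0% |
| 0.25 | 31–50% | 0.048 | 80.9 v 81.3% | 10.9 v 10.8 | 95.2% |
| 0.5 | 23–59% | 0.044 | 81.4 v 82.9% | 10.9 v 10.5 | 95.7% |
| 0.75 | 16–68% | 0.037 | 82.2 v 85.2% | 10.9 v 10.2 | 96.3% |
| 1.0 | 11–75% | 0.030 | 83.1 v 87.8% | 10.9 v 9.8 | 97.0% |

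**Step 3. Simulation at a site SD of 15 points.** Assumptions: 489 completers in seven unequal sites (14 to 170 where sizes were specified), with site rates varying around 40%. Ranges are over repeated simulations, the largest of 20,000 trials. Monte Carlo error at 6,000 trials is about 0.3 points for type I error and 0.5 for power.

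| Allocation | Type I error, unstratified v stratified | Power, unstratified v stratified |
|---|---|---|
| Patient-level blocks | 4.1–4.5% v 4.9–5.3% | 82.5–83.5% v 84.3–85.1% |
| Same-arm runs of 8–18 | 5.9–6.6% v 4.9–5.4% | 79.1–80.2% v 81.9–82.2% |

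At an SD of 8 points the two analyses are about equal.

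**Step 4. Same-arm runs over the logit range.** With 4,000 trials per case and equal to unequal sites, the unstratified H2a alpha is 5.7–6.3% at logit SD 0.5 and 6.5–9.3% at 1.0. The stratified test stays at 4.8–5.4%. For H2b at logit SD 1.0, the unstratified interval covers 91.8% (equal sites) or 91.3% (unequal), against 94.7% or 94.5% when stratified.

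**Step 5. The price of stratifying.** Under same-arm runs with no site spread, stratified v unstratified H2a power was 79.7 v 80.7% (equal sites), and 79.0 v 80.3%, 78.2 v 80.2% and 77.2 v 79.3% (unequal sites). That is a loss of about 1 to 2 points. At an SD of 8 points one simulation gave 79.3 v 80.0%.

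**The case against.** The strongest reply is that nothing in the documents shows a problem. They give no site success rates and no planned site sizes, so every figure beyond Step 1 rests on assumptions. At modest spread (31–50%) the loss is 81.3 − 80.9 = 0.4 power points. This stands, and it limits the point to a conditional one.

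A reader might infer that the error rates are wrong and the 80% power is missed. The documents do not support that. The 80% reproduces. Under patient-level blocks the unstratified test errs on the safe side and keeps more than 80% power, and under same-arm runs at an SD of 15 points it stays close to 80%.

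A reader might also infer that the plan ignores site altogether. That cannot be said of the H2a logistic regression, whose covariates are unspecified. It is true of the named tests and of the H2b interval.

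The inflation under same-arm runs is also fragile. In one simulation at an SD of 15 points, Fisher's exact test rejected 5.4% of the time under the null, the unstratified z test 5.9% and the stratified test 4.9%. The plan's passage on virtual groups reports an average group size of about 4. If same-arm runs were that short (3 to 5 assumed), the inflation disappears: 4.4% for the z test and 3.9% for Fisher's. Group size at sessions is not necessarily the length of an allocation run, so this does not settle the matter.

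Finally, stratifying is not free in every case, as Step 5 shows. That also stands.

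**Conclusion.** The point holds as a minor improvement. Randomization is stratified by site; the named H2a tests and the H2b interval are not, and H2b has no adjusted alternative.

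If success varies between sites with an SD of about 15 points, the unstratified H2a test is mildly conservative under patient-level blocks (type I error about 4 to 4.5%, about 1.5 to 2 power points lost). It may be mildly anti-conservative under same-arm cohorts of 8 to 18 (about 6%). With little spread the choice hardly matters. The site spread, the site sizes and the length of same-arm runs are all assumptions.

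This is not a demonstrated error in the stated power. Nor should a stratified test be read as a cure for cohort-wise allocation: it removes differences in site mix, but not clustering by treatment cohort or drift over calendar time.

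**What to change.** - **H2a:** replace the Chi-square and Fisher's exact tests with one Cochran-Mantel-Haenszel test stratified by site, or name site as a term in the planned logistic regression and make that the analysis of record. In either case, list the covariates.
- **H2b:** report a site-stratified Mantel-Haenszel risk difference with its 95% confidence interval, and name the variance formula. With unequal sites and individual allocation, the stratified interval simulated here covered 94.3–94.4%, slightly below nominal.
- **Allocation:** reconcile the block randomization in the opening of the Methodology section with the open-arm cohorts in its Randomization paragraph, because the direction of the error depends on which applies. If cohorts were used, address clustering by cohort and calendar time separately.

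**Cost:** SAP wording only, since site is known for every participant. The statistical price is about 1 to 2 power points if allocation ran in long same-arm cohorts and sites differ little or not at all. No power loss appeared under patient-level blocks.

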### *Aim 2: Compare the Effectiveness of (1) Taper + CPSMP, or (2) Taper + pain-CBT, or (3) No Behavioral Treatment (Taper Only) within the Context of Patient-Centered Collaborative Opioid Tapering.*

Hypothesis 2a. Participants receiving behavioral interventions (Taper + pain-CBT or Taper + CPSMP) will be more likely to reduce their opioid dose than those in the Taper Only group (no behavioral intervention).

Hypothesis 2b. There will be no significant differences in dosage reduction or the percentage of participants reducing dosage between the Taper + pain-CBT and Taper + CPSMP groups.

Hypothesis 2c. Participants in the Taper + pain-CBT group will experience less pain, less pain interference, and decreased depression compared to those in the Taper + CPSMP or Taper Only groups.

Hypothesis 2d. Participants in the Taper + CPSMP group will show greater improvements in satisfaction with social roles and activities and self-efficacy compared to those in the Taper + pain-CBT or Taper Only groups.

*Exploratory Hypothesis 2e.* Opioid escalation will be less common among participants in the behavioral intervention groups (Taper + pain-CBT or Taper + CPSMP) compared to those in the Taper Only group.

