### ***Study Outcomes***

#### ***Primary Outcome (Aim 1) – Taper Success at 12 months***

Taper success will be defined as a  $\geq 50\%$  reduction in MEDD from baseline to 12 months without significant pain intensity increase ( $\leq 1$ -point increase) or no opioid increase with significant pain relief ( $\geq 2$ -point decrease in pain intensity). Please see Appendix A, Data Measurement Plan, for more details.

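### The plan says a 95% CI will determine equivalence of pain-CBT and CPSMP (Hypothesis 2b), but gives no margin or reading rule and otherwise sets the comparison up as estimation

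*Combined protocol and SAP*

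**What the plan says.** Four places in the combined protocol and SAP bear on this comparison.

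- **Study Goals and Objectives, Aim 2, Hypothesis 2b** expects "no significant differences in dosage reduction or the percentage of participants reducing dosage" between the two behavioural arms.
- **Sample Size Calculations and Study Power, Hypothesis 2b** says that 163 participants per arm "yield an expected 95% CI of [-11%, 11%] for estimating the difference in taper success rates", "assuming a taper success rate of 50% in both arms". It states neither a margin nor a power for equivalence.
- **Statistical Analysis Plan, Hypothesis 2b entry** will estimate the difference in success rates "using an intention-to-treat procedure and construct 95% CIs for the difference".
- **Statistical Analysis Plan, paragraph after the Hypothesis 2d entry** says the same difference "will be assessed with 95% confidence intervals (CI) to determine equivalence".

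The Access and Intervention Participation and Sensitivity Analysis paragraphs add an as-received comparison and a version of success based on a 30% dose reduction. Neither is a margin for the difference between arms.

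**The concern.** Determining equivalence means reaching a verdict, and a verdict needs a margin and a rule. The plan supplies neither, and its two other statistical descriptions of the comparison call only for an estimate. The later sentence therefore promises a conclusion that the rest of the plan does not set up.

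The only wording in the document that resembles a criterion is the expectation of no significant difference in Hypothesis 2b. If that filled the gap, failure to detect a difference would be reported as equivalence, and this becomes easier as the data become less precise. The Study Arms section says no evidence currently guides a choice between the two programs, and the Project Summary promises patients and prescribers evidence for such choices. An unsupported statement of equivalence would bear directly on that choice.

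**Working it through.** **Inputs.** The sample size section gives 163 month-12 completers per arm, 50% success in both arms, a two-sided 95% interval and a total enrolment of 594. Equal thirds of 594 give 198 per arm. The 198 figures assume that every enrolled participant supplies an outcome, with success averaging 50%. All figures treat participants as independent.

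**The plan's own figure.** Half-width = 1.96 × √(2 × 0.5 × 0.5 / n).
- n = 163: 1.96 × 0.0554 = 0.109, which matches the stated ±11 points.
- n = 198: 1.96 × 0.0503 = 0.098.

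The stated interval is correct. It describes precision and is not a margin.

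**If equivalence were read as an interval that includes zero.** Take a true difference of 10 points, 45% v 55% (an illustrative assumption). SE = √(2 × 0.45 × 0.55 / n), and the chance of including zero is Φ(1.96 − 0.10/SE), the other tail being negligible.
- n = 163: SE = 0.0551, 0.10/SE = 1.815, Φ(0.145) = 0.56.
- n = 198: SE = 0.0500, 0.10/SE = 2.00, Φ(−0.04) = 0.48.

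Exact binomial calculation gives 0.55 and 0.49. By the same method at 163 per arm, the chance is 95% for identical arms, 85% for a 5-point difference and 31% for 13.5 points. The last is the size of difference that the plan powers for Hypothesis 2a (40% v 53.5%).

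**The worst interval that still includes zero.** Let D be the largest observed difference, centred on 50%, whose interval just reaches zero: D = 1.96 × √(2 × (0.5 + D/2)(0.5 − D/2) / n). The upper limit is then 2D.
- n = 163: D = 0.108, upper limit 0.216.
- n = 198: D = 0.098, upper limit 0.196.

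**If a margin were set instead.** Suppose equivalence requires the whole 95% CI to lie inside ±m. With identical arms at 50%, power = 2Φ(m/SE − 1.96) − 1. Setting this to 0.80 gives m = (1.960 + 1.282) × SE.
- n = 163: 3.242 × 0.0554 = 0.180.
- n = 198: 3.242 × 0.0503 = 0.163.

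Exact binomial checks give 0.797 for ±18 points at 163 and 0.791 for ±16 points at 198.

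**A separate, smaller point: the endpoint.** Aim 2 words Hypotheses 2a and 2b in terms of dose reduction. The sample size section analyses taper success for both, and the SAP compares success rates, which I take to be taper success. Under the Primary Outcome definition, success can also be reached by "or no opioid increase with significant pain relief", that is, with an unchanged dose. Similar success rates would therefore not show similar dose reduction.

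**The case against.** The best defence is that the word equivalence is loose. The plan commits to a 95% CI, so any imprecision would be visible to readers, and Hypothesis 2b is a secondary comparison. That limits the seriousness of the point but does not remove it: the sentence still announces a conclusion, and if the word is only loose, deleting it costs almost nothing.

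A reader might infer several stronger things that the documents do not support.

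- **That the plan has adopted non-significance as its rule for equivalence.** Hypothesis 2b states an expected result, and the equivalence sentence does not refer to it. The 56% and 48% figures are therefore conditional on that reading.
- **That ±11 points is the intended margin and the trial has almost no power for it.** The sample size section offers the interval "for estimating the difference in taper success rates between the Taper + pain-CBT and Taper + CPSMP arms". Using a trial's own expected half-width as its margin gives near-zero power almost by construction (about 2% at 163 per arm, 4% by binomial simulation), so that figure says little about the design.
- **That an interval reaching 20 points or more is the likely result.** It requires an observed difference right at the significance boundary.
- **That the dose v success mismatch is peculiar to Hypothesis 2b.** It applies equally to Hypothesis 2a.

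**Conclusion.** The point stands. An equivalence conclusion is announced with no margin and no reading rule, and the plan's other descriptions of the comparison support estimation only. There is no arithmetic error in the plan. The missing rule matters because it would decide the conclusion. If an interval including zero were enough, a true 10-point difference would be called equivalent in about 56% of trials at 163 per arm or 48% at 198, and the interval could at worst still include about 20 to 22 points.

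These figures rest on success near 50%, independent participants and, at 198, complete outcomes. Correlation within treatment groups would widen the intervals; the documents give no intraclass correlation, so this is not quantified. The change should be made, but the comparison is secondary and nothing here calls the trial's other analyses into question.

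**What to change.** In the Statistical Analysis Plan paragraph after Hypothesis 2d, delete the words that give the interval the purpose of determining equivalence. Report the pain-CBT v CPSMP difference with its 95% CI, as the Hypothesis 2b entry and the sample size section already plan. Reword Hypothesis 2b under Aim 2 as estimation, and state that an interval including zero is not evidence of equivalence.

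If an equivalence claim is kept, fix a clinically justified margin before unmasked results are seen, require the whole 95% CI to lie inside it, and state the power at that margin in the sample size section. With a 95% CI, a margin narrower than about ±18 points at 163 per arm, or ±16 at 198, would have less than 80% power even if the arms were identical.

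For the endpoint, word the conclusions for both Hypotheses 2a and 2b as taper success. Alternatively, add a between-arm estimate of 12-month MEDD change with its 95% CI. The Methodology section (end of the Monthly CHOIR surveys text) already plans opioid data at baseline, 6 and 12 months, so no new collection is needed. If the percentage of participants reducing dosage is kept as an outcome, it needs a definition, because Hypothesis 2b gives no threshold.

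The cost is wording under Aim 2 and in the Statistical Analysis Plan, plus the sample size section if equivalence is kept, and a weaker Hypothesis 2b conclusion than the plan now implies.
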